8.7 Dose Limitations for Normal Tissue

The following normal tissues will be contoured if they are evident within 5 cm of the liver on the planning CT scan:

- Spinal cord
- Esophagus
- Heart/Pericardium
- Stomach
- Duodenum
- Bowel, large/small
- Kidney, left/right
- Chestwall/rib
- Liver

All OAR should be contoured 1cm above and below the PTV with the exception of the liver which should be contoured in its entirety. The following constraints are recommended for a **5-fraction regimen** but can be modified at the discretion of the treating physician:

Serial Organ	Volume	Volume Dose (Gy)	Avoidance Endpoint (Reference)
Spinal Cord	<0.03 cc	28	Myelitis (Timmerman)
	<0.35 cc	22	Myelitis (Timmerman)
	<1.2 cc	15.6	Myelitis (Timmerman)
Esophagus (Non-adjacent wall)	<0.03cc	35	Stenosis/Fistula (Timmerman)
	<5 cc	27.5	Stenosis/Fistula (RTOG 0813)

Heart/Pericardium	<0.03 cc	38	Pericarditis (Timmerman)
	<15 cc	32	Pericarditis (RTOG 0813)
Stomach	< 0.5cc	35	Ulceration/Fistula (Timmerman)
	< 5cc	26.5	Ulceration/Fistula (Timmerman)
Duodenum	< 0.5 cc	30	Ulceration (RTOG 1112)
	< 5 cc	18.3	Ulceration (Timmerman 2006)
Bowel	< 0.03 cc	40	Ulceration (Timmerman)
	<20 cc	28.5	Colitis/Fistula (Timmerman)
Renal hilum/Vascular Trunk	<15 cc	23	Malignant Hypertension (Timmerman)
Chest wall	<0.03 cc	57	Pain or Fracture (Timmerman)
	<5 cc	45	Pain or Fracture (Timmerman)
Parallel Organ	Volume	Volume Dose (Gy)	Avoidance Endpoint (Reference)
Ipsilateral Kidney	< 130 cc	14.5	Basic Renal Function (Timmerman)
Total Kidney	< 200cc	18	Basic Renal Function (Timmerman)
Liver	<700 cc	21	Basic Liver Function (Timmerman)

The following constraints are recommended for a **10-fraction regimen** but can be modified at the discretion of the treating physician:

Serial Organ	Volume	Volume Dose (Gy)	Avoidance Endpoint (Reference)
Spinal Cord	<0.03 cc	30Gy	Myelitis (Milano)
Esophagus	<0.03 cc	40Gy	Stenosis/Fistula (Milano)
Stomach	<0.03 cc	50Gy	Ulceration/Fistula (Milano)
Duodenum	<0.03 cc	40Gy	Ulceration/Fistula (Milano)
Bowel	<0.03cc	50Gy	Ulceration/Fistula (Milano)

Kidneys	<50%	16Gy	Basic renal function (Milano)
Parallel Organ	Volume	Volume Dose (Gy)	Avoidance Endpoint (Reference)
Liver-GTV	≥1000cc		Basic Liver Function (Milano)
Liver	mean	13Gy	Basic Liver Function (RTOG 1112)

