8.4 Localization, Simulation

All patients will undergo standard of care CT-based treatment planning in custom made immobilization devices. CT scan range must allow simultaneous view of the patient anatomy and fiducial system for stereotactic targeting (if used) and be adequate to ensure contouring of all targeted lesions, as well as necessary organs at risk (OAR). High-resolution CT scans should be obtained with uniform slice thickness of $\leq 3\text{mm}$ throughout.

The use of IV contrast is preferred. If there is a contraindication for IV contrast an abdominal MRI must be available for treatment planning. The use of other contrast agents is left to the discretion of the treating oncologist. If possible, the use of triphasic (arterial, portal venous, and delayed imaging) is recommended using a flow rate of 4-5ml/sec and 175ml of contrast.

Regions of high vascular contrast in the planning dataset are recommended to be converted to water equivalent density if used for planning (at the discretion of the treating physician). Planning datasets without intravenous contrast may be used for dose calculation.

Ideally a liver-specific MRI will be available and possibly fused with the treatment planning CT scan for target delineation.

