8.6 Treatment Planning/Target Volumes

CT images (ideally triphasic images) will be registered to MRI images (by soft tissue alignment) to assist in contouring the GTV. Registration will be performed with the best fit liver-to-liver image registration focusing on the region of the PTV if deformation or rotation occurs between scans.

The GTV represents the target lesion and should be identified on the arterial, portal venous, and delayed CT image sets (if multiple phase CT images are available) as well as on MRI images.

An ITV expansion of the GTV will be created to fully account for the magnitude of the motion observed in the 4D simulation evaluation. If multiple contrast phases are available from CT simulation these will be registered to bony anatomy to verify that the GTV remains encompassed by the ITV.

The ITV will be expanded by 5-10mm radially and 7-10mm superior/inferiorly to arrive at the PTV.

The treatment dose is 50 Gy in 5 or 10 fractions over 2 or 3 weeks, respectively. Lesions in close proximity to a GI structure (colon, small bowel, duodenum, stomach), in a patient with Child-Turcotte-Pugh (CTP) classification B, or a patient with prior radiotherapy to the abdomen will be treated with 50Gy in 10 fractions. Fractionation determination is at the discretion of the treating physician.

Conformal 3D or arc radiotherapy, IMRT or VMAT are acceptable methods of treatment delivery.

All patients must be imaged prior to treatment with volumetric imaging.

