8.6.2 Dose calculations

All dose distributions shall include corrections for tissue heterogeneities. RPC approved algorithms must be used. All doses should be reported in terms of dose-to-water and not in terms of dose-to-medium. Successful treatment planning will require accomplishment of all of the following criteria: These criteria will be assessed on dose calculated independently for each lesion (i.e., not from composite dose calculations) if more than 1 lesion is present.

1. **Normalization:** The treatment plan should be initially normalized such that 100% corresponds to the maximum dose within the PTV (MAXPTV). While this point will typically correspond to the PTV center of mass, it can be located elsewhere within the PTV.
2. **Prescription Isodose Surface Coverage:** The prescription isodose surface will be chosen such that 95% of the target volume (PTV) is conformally covered by the prescription isodose surface. Doses less than 95% of the prescription dose are restricted to the outside edges of the PTV. The prescription isodose surface selected MUST be $\geq 60\%$ and $\leq 90\%$ of the dose maximum within the PTV (MAXPTV). The MAXPTV corresponds to the normalization point (100%) of the plan as noted in number 1 above.
3. **Target Dose Heterogeneity:** Rather than prioritizing target dose homogeneity, HIGRT treatment planning prioritizes adequate minimum target coverage and rapid dose fall-off gradients outside of the target. Hot spots within targets are generally accepted without consequence since targets are mostly tumor. The only exception is when the hotspot within the PTV also intersects an OAR.
4. **Critical Organ Doses:** Respect all critical organ dose-volume limits listed below
5. **High-Dose Spillage:**

- a. **Location:** Any dose > 105% of the prescription dose should occur within the PTV and not within the normal tissues outside the PTV.
- b. **Volume:** Acceptable isodose distributions should be as conformal as possible. To this end the ratio of prescription isodose volume to PTV should be as small as possible.
 - i. The ratio of the prescription isodose volume to the PTV volume should ideally be < 1.2.

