 - ii. Guidelines for the ratio of the 50% prescription isodose volume to the PTV volume (R50%) and for the maximum dose at 2cm (D2cm) from the PTV. Because it may become more difficult to restrict the 50% isodose volume when dose is summed from treatment of multiple lesions, this ratio should be evaluated for dose calculated for a single lesion (i.e., not for composite dose). Additionally, the 50% isodose volume may be elongated deliberately in order to avoid OAR thereby making it difficult to meet the constraint guidelines. This is acceptable as long as normal tissue constraints are met.

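### Cutting organ contours 1 cm above and below the PTV can make a 5-fraction plan appear to meet the duodenum <5 cc limit when the whole duodenum exceeds it; few patients are exposed

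*Combined protocol and SAP*

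**What the plan says.** Section 8.7 first lists the organs to draw when they lie within 5 cm of the liver, the duodenum among them. It then sets how much of each to draw: "All OAR should be contoured 1cm above and below the PTV with the exception of the liver which should be contoured in its entirety".

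The 5-fraction table in 8.7 has two duodenum rows, both absolute volumes: under 0.5 cc at 30 Gy and under 5 cc at 18.3 Gy. The limits are recommended, and the treating physician may modify them. Section 8.6.2 nevertheless includes among its criteria for successful planning: "Respect all critical organ dose-volume limits listed below". It also accepts that "the 50% isodose volume may be elongated deliberately in order to avoid OAR thereby making it difficult to meet the constraint guidelines", and adds: "This is acceptable as long as normal tissue constraints are met".

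Section 8.6 prescribes 50 Gy in 5 or 10 fractions. It directs three groups to 10 fractions: lesions close to a GI structure (the duodenum is named), Child-Pugh B patients, and patients with prior abdominal radiotherapy. It then says: "Fractionation determination is at the discretion of the treating physician".

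**The concern.** An absolute volume read from a truncated contour can equal the whole-organ value or fall below it, but never exceed it. Any error therefore runs toward passing the plan. The contrast with the liver makes 1 cm read as a cut-off, and nothing marks it as a minimum. The 5 cm sentence decides which organs are drawn, not how far.

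The listed harm for this row is ulceration. The physician may relax the limit, but that judgement needs a correctly measured duodenal volume. Section 8.6.2 also relies on the organ limits as its condition for accepting a stretched 50% isodose, so a low reading weakens that check.

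**Working it through.** The plan gives no figure of its own to reproduce here. The check has two parts.

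**1. Can the 18.3 Gy isodose pass the cut?** 18.3/50 = 36.6% of prescription, so it lies outside the 50% isodose.
- *Linear superior/inferior fall-off (assumed).* Distance = (100 − 36.6)/gradient. At 4 to 6% per mm the isodose reaches 1.58 to 1.06 cm, beyond the cut. At 8 to 10% per mm it reaches 0.79 to 0.63 cm, inside it.
- *Spherical PTV with exponential fall-off (assumed).* With PTV radius 1.5 cm and R50% (50% isodose volume over PTV volume) of 2.5 to 3, it ends within 1 cm on either linear or exponential extrapolation (0.7 to 0.96 cm). With radius 2 to 3.5 cm and R50% 3 to 6 it reaches about 1.1 to 4.2 cm.

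**2. Can both duodenum rows be passed falsely?**

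Inputs from the documents:
- Lesion up to 5 cm (6.1).
- PTV margin: "The ITV will be expanded by 5-10mm radially and 7-10mm superior/inferiorly to arrive at the PTV" (8.6).
- 50 Gy prescribed (8.6).
- Duodenum rows and the liver row of 700 cc at 21 Gy (8.7), the latter read as a maximum.

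Assumptions:
- Lesions of 2, 3, 4 and 5 cm; 1.0 cm margin; 50 Gy at the PTV edge.
- R50% of 3, 4, 5 and 6, because no values appear in the text available. This gives 16 settings.
- Duodenum as a horizontal tube 2.5 cm wide and 12 cm long below the PTV, with only the part within 1.0 cm of the PTV recorded.

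Formulas: r = lesion/2 + 1.0; d50 = r × (R50^(1/3) − 1); dose(d) = 50 × 2^(−d/d50).

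Example, 3 cm lesion and R50% 4:
- r = 2.5 cm; d50 = 2.5 × 0.587 = 1.47 cm.
- 18.3 Gy distance = 1.47 × log2(50/18.3) = 2.13 cm.
- Liver screen: (4/3)π(2.5 + 1.47 × log2(50/21))³ − (4/3)π(1.5)³ = 342 − 14 = 328 cc, so the setting is kept.
- At a 0.9 cm gap, 0.4 cc is recorded against a true 8.9 cc.

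The liver screen (under 700 cc) keeps 11 of 16 settings, at 121 to 608 cc. A false pass means both duodenum rows are met on the recorded volume while at least one is broken on the true volume.

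| Gap (cm) | 0.5 | 0.6 | 0.7 | 0.8 | 0.9 | 1.0 | 1.2 | 1.5 | 2.0 |
|---|---|---|---|---|---|---|---|---|---|
| False passes of 11, isotropic | 0 | 2 | 2 | 4 | 8 | 8 | 6 | 3 | 1 |

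- At 0.5 cm the 18.3 Gy row alone is misread in 6 of 11, but the 30 Gy row already fails on the drawn part, so those plans are flagged.
- At 0.9 cm the eight false passes record 0.4 to 0.6 cc against a true 6.6 to 24.2 cc.
- From 1.0 cm outward nothing is recorded. Those columns apply only if the rule is taken literally as no contour beyond the cut.

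Sensitivity:
- Superior/inferior fall-off distance at 80% of the isotropic value: 5 of 11 at 0.9 cm and 4 of 11 at 1.0 cm.
- At 60%: 1 of 11 at each, and at most 3 of 11 at any gap.
- PTV margin 0.7 cm: 9 of 14 at 0.9 cm and 8 of 14 at 1.0 cm.
- Tube run vertically: 7 of 11 at 0.9 cm, at most 1 of 11 from 0.5 to 0.8 cm.

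Other organs under the isotropic model: stomach, at most 3 of 11 at any gap tested; bowel (20 cc row), 0 of 11; heart, at most 1.2 cc missed against a 15 cc limit. The 40 Gy isodose stays within 0.3 to 0.9 cm of the PTV, so the 10-fraction GI rows are unaffected.

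**The case against.** **The 10-fraction rule covers most of the exposed group.** A duodenum within about 1 cm of the PTV is the kind of case it targets. What remains is a Child-Pugh A patient without prior abdominal radiotherapy whose physician does not judge the lesion close, or overrides the default. This stands and makes the group small. It does not empty it, because closeness is undefined and the choice is discretionary.

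**The counts rest on assumed fall-off.** Section 8.6.2 announces guidelines for R50% and for dose at 2 cm, but no values follow in the text available. They may have been in a table lost in PDF reading, so their absence is not a fault of the plan. The kept settings put 21 to 51% of prescription at 2 cm, and whether such plans would meet the guidelines cannot be known. Coplanar beams are allowed and steep gradients are a stated priority, so superior/inferior fall-off may be sharper than isotropic. This stands, and it is why 8 of 11 cannot be given alone.

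**The 0.9 cm result is finer than a CT slice.** Section 8.4 permits slices up to 3 mm. Rounding the drawn range outward to 1.2 cm lowers 8 of 11 to 5 of 11; rounding inward to 0.9 cm leaves 8.

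**The wording is soft.** The sentence says should, could be read as a minimum, and feeds limits that may be modified. This lowers the severity but does not correct the measurement.

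**Elongation is allowed in order to spare organs.** A reader might infer that the plan permits stretching dose into an undrawn duodenum. The documents do not support that: they give no direction for the elongation.

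**Conclusion.** The point holds in limited form. Under-recording follows from the rule itself whenever the 18.3 Gy isodose passes the cut with duodenum there. A false pass of both duodenum rows is plausible for a 5-fraction plan with duodenum about 0.6 to 1 cm above or below the PTV, and further out only on the literal reading. The modelled share at 0.9 cm runs from 8 of 11 down to 1 of 11 across the three fall-off assumptions, and reaches none when fall-off is steep or the PTV small.

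Three stronger inferences are not supported. The fractions count modelled settings and are not a rate among enrolled patients, for which the documents give nothing. The problem is not general to all organs or to both regimens. It also leaves the sample size, alpha and primary quality-of-life analysis unchanged. It is worth correcting because the error favours passing a safety limit and the remedy is cheap.

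**What to change.** Replace the sentence in 8.7 with: *Contour the liver in its entirety. Contour every other listed organ at least 1 cm above and below the PTV and, where the table for the chosen regimen lists a limit for that organ, through all slices receiving the lowest dose listed.* The last part is checked after the first dose calculation. The measured 18.3 Gy volume then equals the whole-organ value. No dose limit changes.

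Also contour both kidneys whole where the 10-fraction percentage limit applies, so that its denominator is the whole organ. This is a measurement correction and not part of the safety point, since truncation there usually overstates the percentage.

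The cost is a few more minutes of contouring per HIGRT plan and occasionally a slightly longer CT range. Section 8.4 already requires a scan range adequate for the necessary organs at risk.

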8.8 Treatment Delivery

Ideally treatment will be delivered on consecutive days, for both the 5 and 10 fraction regimens. It is recommended that all treatment be completed in 2 weeks (for 5 fraction regimen) and 3 weeks (for 10 fraction regimen).

8.9 Localization Using Daily IGRT

Patients require daily image guidance prior to treatment delivery. Orthogonal kV imaging to align bony anatomy (and fiducials if present) followed by cone-beam CT to align soft tissue anatomy is ideal.

Additional IGRT may be employed at the discretion of the treating physician (i.e., orthogonal kV imaging prior to required volumetric imaging or volumetric imaging even if only orthogonal kV imaging is required).

9. IMAGE GUIDED ABLATION TECHNIQUES

9.1 Type, Classification, Location, and Short Description

Subjects will be scheduled for PLA as an outpatient treatment. Each subject will report to the Radiology department at the hospital on the day of the treatment for patient registration and nursing intake into the pre-procedure area as per normal hospital protocol. PLA is administered as a single treatment.

The procedure may be performed under moderate sedation or general anesthesia based on operator discretion. All patients will be maintained NPO after midnight the preceding evening. Patients on extensive medications, in particular hypertension and cardiac medications may take these medications in the morning with a small quantity of water. Insulin-dependent diabetic patients should administer half of their usual morning insulin dose. Patients will be administered prophylactic anti-emetic (ondansetron 4mg IV) and antibiotics (Unasyn 3g IV).

The patient positioning for ablation will be determined by the operator based on the location of the lesion. With the patient in position on the CT table, a preliminary non-contrast CT will be performed for localization of the target tumor and to allow planning for an appropriate percutaneous approach. Administration of intravenous iodinated contrast may be deemed necessary for inconspicuous lesions on the preliminary CT scan. An ultrasound will also be performed for localization of the target lesion. Ultrasound should be the first choice primary modality for antennae guidance with CT-fluoroscopic guidance as second choice. The operative site is cleansed, prepped and draped in sterile fashion. After infiltration of the target site with 1% lidocaine, a small skin incision is made at the correct skin entry site with a #11 scalpel. For lesions well-visualized with ultrasound, real-time sonographic guidance is then utilized to guide the microwave antennae into the lesion. CT-fluoroscopy is used for confirmation of positioning and adjacency to critical structures. For lesions inconspicuous on ultrasound, CT-guidance is initiated and an image is taken with the localizer needle in place to identify proper table position and needle angle. Repositioning can be performed with the localizer needle if necessary. The microwave antenna is then guided into the lesion using real-time CT fluoroscopic guidance. If there is concern for non-target ablation of adjacent structures, adjunct techniques such as infusion of artificial ascites, hydrodissection, or intentional pneumothorax may be utilized.

9.2 Equipment/Imaging

The PLA generators to be used include the Neuwave system, Covidien Emprint, Perseon system, Amica and Boston Scientific. The specific microwave antennae utilized and the number will be at the discretion of the operator. MVA will be performed under ultrasound or CT guidance as per above (section 10.1).

CT images of the treatment antenna(e) placement within the target lesion must be obtained to document final positioning prior to treatment. These images should also be among the images transferred to imaging archive. These images are necessary to ascertain the technical success and quality of treatment. Follow up CT scan will also be obtained to evaluate for pneumothorax, hematoma or other acute complications (treated per institutional guidelines if present).

9.3 Dose specifications

Up to 3 microwave antennae will be utilized. Once the microwave antennae are adequately positioned, the antennae are connected to the generator and microwave ablation is then performed based on the individual generator IFU with power and time settings at operator discretion. For larger lesions, multiple overlapping ablation zones may be performed based on the operator discretion to ensure adequate thermocoagulation of the target lesion. The ablation zone, as evidenced by the sonographic 'echo cloud' will be monitored during ablation. If it is determined that there is incomplete tumoral coverage, repositioning or addition of probes may be performed. The MVA aim is to obtain a 0.5 cm ablation margin around tumor.

9.4 Post-PLA monitoring

Immediately following the intervention, the patient will be monitored in a recovery area with a dedicated nursing staff; any early procedure-related adverse event will be documented. After appropriate post-procedure monitoring, the patient is discharged to home if all necessary criteria for discharge are met.

10. PATIENT ASSESSMENTS

As per standard of care, all patients will undergo laboratory evaluation and imaging to determine current liver status as well as extent of HCC.

10.1 Pretreatment Evaluations/Management

Baseline imaging and lab work should be complete within 8 weeks of signing study consent and include

- Multi-phase contrast enhanced CT or MRI of abdomen
- CMP or BMP and LFTs (including Total Bilirubin, Albumin)
- CBC
- INR
- Hepatitis serologies (pre-existing serologies will be accepted)
- AFP
- CT chest or PET-CT
- Serum pregnancy test (if woman of childbearing age)

10.2 Screening Examination

The screening examination will take place prior to any scheduled procedures. An informed consent must be signed by the patient before any study screening procedure takes place. If standard of care evaluation procedures have been obtained and are within the screening evaluation time points, the SOC procedures do not need to be repeated and may be included in the screening examination.

If applicable, pregnancy test will be obtained per institutional policy.

10.3 Treatment Period

Treatment period will be from start to finish of HIGRT or date of ablation based on randomization. Assessment will be performed by the study key personnel at baseline then months 1, 3 and 6 post-treatment for QOL surveys. They will also undergo weekly assessment by radiation oncologist during radiotherapy.

Restaging imaging and labs (LFTs, and AFP, INR) will be performed as per standard of care for HCC (typically 1 month post-treatment, 3 months post treatment and then every 3 months thereafter). Deviations from standard of care follow up for patients are at the discretion of the treating physicians.

